2-Week Visit. Patients will undergo a follow-up appointment at Week 2 with a study clinician, where health and adverse events will be assessed, and patients will complete questionnaires and will be reminded to increase medication dose. Participant may receive a ride to and from the study visit if requested.

4-Week Visit. Patients will undergo a second follow-up appointment immediately after the four-week treatment period with a study clinician, where we will assess back pain, general health, and adverse events. On the same day or as close as possible depending on scheduling, patients will be re-scanned, using identical protocols, to evaluate the hypothesis that CBD reduces glial activation. We will also repeat the questionnaires administered during the baseline visit to assess any changes in subjective pain. While this study is focused on mechanisms, and is not powered to detect a clinical effect, collecting pain scores will allow us to start evaluating the potential clinical significance of any reductions in neuroinflammation we will observe, and also provide important preliminary data for a subsequent clinical trial focused on efficacy. We will also take a small sample of blood for a follow-up liver function test. Participant may receive a ride to and from the study visit if requested.

6-Week Call. We will conduct a follow-up call 2 weeks after the discontinuation of the study medication. In this call, we will assess back pain, general health and adverse events.

DATA ACQUISITION AND ANALYSES

MR-PET scanning will be performed at 3 Tesla, using Siemens TIM Trio whole-body MRI with head PET camera, and/or Siemens Verio whole-body MRI, whole-body PET camera (Biograph mMR).

PET

During each visit, [¹¹C]PBR28 (up to 15 mCi, corresponding to ~3.7mSv) will be injected intravenously with a slow bolus over a 30-60s period⁶⁴. This dose is compatible with a longitudinal study, because the total radiation of maximum ~7.4mSv received by the subjects participating in two scans will be significantly less than the maximum allowed annual whole-body dose set by the U.S. Food and Drug Administration at 5 REM, i.e., 50mSv). The catheter will be flushed post-injection with 0.9% saline solution. Dynamic data will be collected over ~120 minutes in list mode, and framed post-collection. Regional uptake of the tracer will be estimated as SUV, SUVR, Vt and/or DVR.

In addition, participants will be asked if they are willing to undergo spinal cord PET imaging, which will take \sim 20-30 minutes extra in the PET scanner at the end of the 90 minutes post-injection. This will not add significant risk, as it will not require extra injection.

MRI

MRI data will be acquired simultaneously to the PET data, and may include some or all of these standard sequences: BOLD fMRI (e.g., for functional connectivity analyses, to

estimate motion parameters), Diffusion-Spectrum or Diffusion-Tensor Imaging volumes (DSI) (to perform tractography analyses); Chemical shift imaging (to estimate brain metabolites); a high resolution structural volume (for anatomical reference, cortical reconstruction, volumetric segmentation, and attenuation correction); in addition to various T1 and T2 weighted structural volumes.

We may collect a 6-minute resting-state connectivity functional MRI scan. The additional MR sequences are only collected when all the core MRI data have been completed early, and the patient still needs to remain in the scanner to complete data acquisition. As mentioned before, this is an integrated PET/MR study, the MRI (including fMRI) data is collected throughout the PET data acquisition, and as such the participant needs to stay in the scanner for the 90 minutes to complete the brain scan. Therefore these additional MR sequences will not affect the duration of the scan. This additional data will be used for ancillary analyses.

Behavioral measures

Before, during and after the scans, subjects may be asked (either verbally, or using a button box connected to a computer) to express various behavioral ratings, including pain intensity, unpleasantness, and anxiety.

BIOSTATISTICAL ANALYSES

If time allows, we may collect resting-state fMRI scans. This will only be collected if core MRI data have been completed early, and the patient still needs to remain in the scanner to complete data acquisition. Therefore, the resting state fMRI will not affect the duration of the scan. All fMRI data will be stored on hard drive and storage clusters. Behavioral data will be recorded and stored in RedCap in preparation for statistical analyses.

In order to address our aim ('Assess the effect of CBD on glial activation and pain), we will perform paired t-tests in cLBP patients before vs after receiving CBD. We will also perform an ANOVA including age and sex as covariates of no interest. Additionally, secondary regression analyses will be performed in order to evaluate the association between imaging and behavioral data (e.g., questionnaire scores, pain duration, etc). For the exploratory assessment of the relationship between imaging and pain measures, we will use multiple regression analysis. We will use a thalamus-targeted region of interest analysis, in which mean SUVRs will be extracted from the voxels within the right and left thalamus labels of the Harvard-Oxford Subcortical Structural Atlas and will be correlated with differences in clinical pain scores from baseline to Week 4. To be consistent in our use of non-parametric methods, we will use a non-parametric regression method, Generalized Additive Models. We will compute residuals adjusting for the effect of genotype. The Ala147Thr polymorphism in the TSPO gene predicts binding affinity

for 11C-PBR28, with the Ala/Ala, Ala/Thr and Thr/Thr genotypes being associated with high, mixed and low affinity binding, respectively. For all analyses, we will adjust for the TSPO polymorphism.

Since the analysis plan requires a pre- and post-scan, we will not include patients with only one scan in the analysis for this pilot study. If the pilot study warrants a larger trial, we will use likelihood based mixed models to produce unbiased estimates of effects in the presence of missing data.

These analyses will be performed voxelwise for the brain data, using methods similar or identical to those we have previously used³⁶, as well for spinal cord data using methods developed by [name]. In addition to these voxelwise analyses, for the spinal cord we will perform region-of-interest (ROI) analyses focused on the spinal cord segments contained in the T11-L1 vertebral levels (as these contain the lower lumbar/upper sacral spinal cord segments).

All voxelwise analyses will be conducted using the FSL suite⁶⁶ for the brain, and using the Spinal Cord Toolbox⁶⁵ for the spinal cord. Group comparisons maps will be thresholded using threshold-free cluster enhancement⁶⁷, and a corrected threshold of p=0.05. All behavioral, demographic and ROI data will be analyzed using Statistica 10.0 (StatSoft Inc., USA), and an alpha level of 0.05.

Consideration of sex as a biological variable

In addition to the aforementioned analyses, the effect of sex will be evaluated using ANOVAs, because animal research suggests the presence of a possible sexual dimorphism in the role of glia in pain (as pain hypersensitivity may be microglial-dependent only in males⁶⁸). The effect of menstrual cycle status will also be evaluated by comparing women in early follicular (day 2-7 after onset of menses) and midluteal (day 20-25 after onset of menses), based on self-report⁶⁹.

POWER ANALYSIS

The purpose of this pilot study is to collect data to adequately power a placebo-controlled trial. The sample size proposed in this study, n = 20, is similar to other cohorts in the PET literature. Most similar to our study is a report in Brain by Loggia et al that showed significant reductions in TSPO binding between 10 chronic back pain patients and 9 healthy controls (Loggia, 2015). This is not a fully-powered trial. If we see a trend toward reduction in TSPO, this will warrant a fully-powered, placebo-controlled trial, for which an adequate sample size will be calculated. We will have dual criteria by which we will consider a trend-level effect to be worthy of consideration of applying for funding to support a larger placebo-controlled trial. If we either (1) observe a TSPO reduction in binding of 5-10% on average from post to pre-

CBD, or (2) observe a clear and consistent reduction in TSPO binding in those patients who also report pain reductions, we will consider this a trend worth pursuit.

RISKS AND DISCOMFORTS

All subjects will undergo a telephone or email screening to attempt to distinguish potential subjects from those not meeting eligibility criteria. Likely candidates will undergo a characterization and training session, which will include a clinical screening procedure. This procedure will involve answering questions about subjects' medical history recording of medical history review and answering questions about their medical situation including liver disease, kidney disease, blood disorders, heart disease, alcohol and opioid use, high blood pressure, asthma and other respiratory disorders.

PET/MR Procedure: The U.S. Food and Drug Administration (FDA) recently gave the first regulatory clearance of a hybrid PET/MRI scanner in the U.S. Additionally, FDA considers investigations of MRI software and hardware operating within FDA specific parameters as non-significant risk device studies. All studies will adhere to these FDA approved safety levels for the Siemens system. These safety parameters include static magnetic field, time varying magnetic fields (dB/dt), specific absorption rate (SAR), and acoustic noise levels. Subjects will be informed about minimal risks of routine high magnetic field and non-ionizing RF radiation involved in MR imaging.

Subjects will also be informed about the PET procedure and the minor risks associated with exposure to radiation. Subjects will also be informed about small space within the magnet and noises made by switching gradients. Subjects will be informed that if they feel uncomfortable with the study, they can choose to terminate the study at any time. They will be informed that their refusal to participate in the study or choosing to terminate it at some point will have no effect on care and treatment received by them at MGH now or in future. The subjects will be informed that their personal information will be protected as per the HIPAA guidelines.

Intravenous catheter: An intravenous catheter will be placed for this study. The subject will feel a slight pinprick, similar to a bee sting, and may feel some discomfort and have some bruising or bleeding at the site where the needle goes in. Depending on the length of time the catheter is in place, a bruise may last for a day or so. Rarely an infection may occur at this site. If infection does occur, it will be treated. About 24 hours after the beginning of the imaging procedures, we will give the subject a phone call to determine whether he or she is experiencing study related issues.

Radiation exposure: The radiation exposure in this study will be small and there is no evidence that it represents a major health risk. If subjects have participated in other research studies in the past 12 months that have involved radiation exposure, they will be

asked to inform the investigators or study staff (by writing initials on the consent form verifying that they have not been exposed to other radiation in the past 12 months). If it is determined that their prior radiation exposure exceeds our current guidelines, they may not be allowed to participate in this study.

We will use [¹¹C]PBR28 produced by the cyclotron/radiochemistry/radiopharmacy facility at the A. A. Martinos Center for Biomedical Imaging. The Martinos Center has studied several hundreds of people with this radioligand and have had no clinically detectable effects or side effects. Given the use of [¹¹C]PBR28 in a small clinical trial, we are in the process of requesting an IND from the FDA.

The IV injection will be administered by a licensed nuclear medicine technologist. Should there be an adverse event, [name] will be responsible for communicating with the IRB within the stipulated time frame.

Imaging will be stopped should any untoward reaction be observed during the imaging session or if the participant so requests for whatever reason. Some subjects find it unpleasant or feel anxious when confined in the enclosed space of the scanner. If this happens, the study will be aborted. Patients will be required to use earplugs to decrease the noise perceived while in the scanner.

EPIDIOLEX (CBD): CBD is an FDA approved medication used to treat epilepsy. According to the FDA briefing document on Epidiolex, dated 04/19/2018, treatment-emergent AEs in controlled trials for Lennox-Gastaut and Dravet syndromes included decreased appetite, diarrhea, irritability, somnolence, fatigue, aggression, pneumonia, rash, and hepatic symptoms, and in a very small number of patients, an increase in suicidal thoughts. Of note, AE related to hepatic function were likely due to the interaction between CBD and anti-epileptic drugs; prescription of an anti-epileptic drug is an exclusionary criterion for this proposed study. Further, CBD may produce pharmacokinetic interaction effects when taken with opioids (Benowitz et al., 1980; Kotlinska-Lemieszek et al., 2015). Any subjects who at baseline had elevated AST/ALT levels but still met the eligibility criteria for the study will undergo a follow-up liver function tests at 2 weeks. In addition, we will perform a liver function test in subjects who at any time point during the study develop clinical signs or symptoms suggestive of hepatic dysfunction.

Given the use of EPIDIOLEX in a small clinical trial, we are in the process of requesting an IND (or an IND exemption) from the FDA.

Questionnaires: Minimal risks associated with completing questionnaires are subject fatigue and the possibility of minor psychological distress associated with answering sensitive questions regarding psychological functioning. Subjects will be instructed to complete the questionnaires to the best of their ability, but will have the option to leave

any question(s) blank. In the unlikely event that evidence of physical or psychological disorder is found, with the individual's permission, the information will be shared with his or her primary care physician who can direct care as needed.

Confidentiality: As detailed, the investigators are quite careful regarding the protection of confidentiality, and multiple procedures are in place to reduce the likelihood of a breach of confidentiality. However, there is a small risk that information about subjects could become known to people outside of this study, and this risk is identified in the informed consent form.

The key investigators will meet quarterly to discuss any potential adverse event and side effects. We will involve the MGH Human Research Committee and Radiation Safety Committee if any additional potential risks arise. Adverse events and unanticipated problems involving risks to subjects or others will be reported to the PHRC in accordance with PHRC adverse event and unanticipated problems reporting guidelines, as well as FDA when appropriate.

POTENTIAL BENEFITS:

It is unlikely that individual subjects will benefit from taking part in this study. While this study is powered to possibly observe a statistically significant reduction in pain due to CBD, it is unclear whether the effect will be clinically meaningful. However, findings from these studies will help advance our understanding of the pathophysiology of pain disorders. In particular, this project will assess the role of microglia in the establishment and/or maintenance of chronic pain, and how this may be affected by CBD.

REMUNERATION:

Subjects will be paid by check at the completion of the study for their participation.

We will pay up to \$525. Payments will be as follows:

- \$75 for the initial behavioral session (Visit 1)
- \$50 for completing daily surveys
- \$200 for each MR-PET scanning visit

If during the imaging visit(s) we cannot inject the subject with the radioligand (e.g., due to a failure in radiosynthesis, or to issues with the scanner) he/she will receive \$50.

If the subject will need to stop the scan early for any reason, he/she will still receive \$50 for his/her time. Additionally, parking fees will be covered as needed.

MONITORING AND QA

The proposed study will be monitored for safety, with monthly staff meetings reviewing adverse events and treatment outcomes and directly reporting any adverse events. The PI will also routinely monitor and assure the validity and integrity of collected data and adherence to the IRB-approved protocol. The trained staff members who carry out the procedures will also carefully monitor the study throughout its duration. The team will evaluate the progress of the study, verify that the rights and well-being of the subjects are protected, verify that the reported study data are accurate, complete and verifiable from source documents, and the conduct of the study is in compliance with the approved protocol and amendments. Outcome monitoring and adverse events will all be reported through appropriate channels of the Human Studies Committee as well to the FDA when appropriate.

If a patient develops clinical signs or symptoms suggestive of hepatic dysfunction (e.g., unexplained nausea, vomiting, right upper quadrant abdominal pain, fatigue, anorexia, or jaundice and/or dark urine), we will promptly measure serum transaminases and total bilirubin and interrupt or discontinue treatment with EPIDIOLEX, as appropriate. We will discontinue EPIDIOLEX in any patients with elevations of transaminase levels greater than 3 times the ULN and bilirubin levels greater than 2 times the ULN. Our physician monitoring group (Drs. [name], [name], [name], and [name]) will consider stopping the study if back pain becomes significantly worse in 3 or more patients. If serum liver enzyme concentrations are significantly elevated (with elevations of transaminase levels greater than 3 times the ULN and bilirubin levels greater than 2 times the ULN) in 2 or more patients, which will be considered serious adverse events, the study will be stopped. In addition, if two or more patients experience any serious adverse event, the study will be stopped.

The Siemens MR-PET scanners have a built-in self-monitoring system that automatically shuts off if parameters exceed safe levels. For backup protection NMR technicians constantly monitor the subjects' physiological signs and the quality of the raw data.

Quality assurance of the scanner's performance is obtained by a daily quality assurance protocol. More extensive quality assurance protocols are performed monthly under the commercial service contract with Siemens Medical Systems. The daily quality assurance protocol consists of an image Signal-to-Noise measurement in a phantom and a stability run which checks the image-to-image variation in image intensity over 600 images using a standard echoplanar imaging sequence with a head-sized phantom. The images are analyzed by the technologist to provide data on SNR (as an absolute, unitless number)

and stability expressed as the peak-to-peak variation in the mean of a 15x15 pixel region of interest (ROI) in the center of the phantom expressed as a percentage of the mean of the ROI. Runs are performed at each of 3 TR values (300ms, 800ms, 1300ms). The time course of the means is also reviewed to check for periodicities (the TR values are chosen so as not to be multiples of one another). If the peak-to-peak variation is greater than 0.5% of the mean value, the Siemens Medical System service engineer is called. In addition to these daily quality assurance tests, the Siemens Medical System service engineer performs quality assurance tests once a month. These tests include a SNR test, a small sample stability test, a gradient stability test, a gradient eddy current test, a shim test, an image uniformity test, and an RF stability test.

BIBLIOGRAPHY

- 1 Merskey, H. & Bogduk, N. Classification of Chronic Pain, Second Edition, Part III: Pain Terms, A Current List with Definitions and Notes on Usage. (IASP Press, 1994).
- Turk, D. C. & Okifuji, A. in *Bonica's management of pain (3rd ed.)* (ed S.M. Fishman, Ballantyne, J.C., Rathmell, J.P.) (Kluwer/Lippincott, Williams & Wilkins, 2010).
- 4 Harstall, C. How prevalent is chronic pain? *Pain: Clinical Updates, X, 1–4.* (2003).
- McCool, W. F., Smith, T. & Aberg, C. Pain in women's health: a multi-faceted approach toward understanding. *J Midwifery Womens Health* **49**, 473-481 (2004).

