After a behavioral visit aimed at determining eligibility, subjects will be scheduled for their first imaging visit, during which they will undergo a simultaneous MR-PET scan. At this visit, subjects will receive CBD. During the drug trial period, subjects will also be sent a daily survey to assess the treatment effect of the medication on their pain. As soon as possible after the end of the 4-week drug trial period, all subjects will be scanned again.

Investigational Agent

Epidiolex, an agent within the anti-epileptic drug class, will be used. Epidiolex, Greenwich Biosciences Inc.'s CBD formulation, is a 100 mg/mL purified oral solution, dissolved in the excipients sesame oil and anhydrous ethanol with added sweetener (sucralose) and strawberry flavoring. The drug is formulated from extracts prepared from Cannabis sativa L. plants that have a defined chemical profile and contain consistent levels of CBD as the principal phytocannabinoid. Extracts from these plants are processed to yield pure (>95%) CBD that typically contains less than 0.5% (w/w) THC. Cannabidiol is the active ingredient in Epidiolex; inactive ingredients include dehydrated alcohol, sesame seed oil, strawberry flavor, and sucralose. Of note, CBD has no psychoactive properties. The empirical formula of Epidiolex is C₂₁H₃₀O₂ and its molecular weight is 314.46. The structure of CBD is provided in the figure below.

[figure not shown]

Figure 1. Cannabidiol Structure

Dose and Exposure

The recommended starting dosage is 2.5mg/kg taken twice daily (5mg/kg/day). Participants will follow a titration schedule, with 5 mg/kg/d in week 1, 10 mg/kg/d in week 2, 15 mg/kg/d in week 3, and 20 mg/kg/d in week 4. Subjects will increase to 20 mg/kg/d on the first day of the final week of the study (week 4) and take Epidiolex at this dose for the remainder of this final week. If participants report AEs (tiredness, dizziness, not tolerating the medication well), the physician will decrease the dose by 5 mg/kg. Participants will be treated for 4 weeks in total.

The 4-week duration of CBD administration is proposed because in the current study, we are investigating an endophenotype of pain-neuroinflammation- which may be detectable before verbal reports of pain reduction, which is notoriously noisy and susceptible to placebo effects. This pilot study will inform us of whether 4 weeks is enough to detect changes in TSPO binding that may precede verbal reports of pain reduction.

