Safety monitoring: As participant suicidality and depression is monitored throughout the study with the C-SSRS and BDI questionnaires, any new or worsening expression of suicidal ideation or Answers of "Yes" to questions 4 or 5 on C-SSRS throughout the study will be evaluation by a licensed clinician member of study staff. The Standard Operation Procedure will be reviewed. To summarize, if any risk for self-harm or suicidality is identified at visit 1, visit 3, or visit 4, the research coordinators will immediately report this to study clinicians, who will determine whether a safety assessment is needed. If a clinician is needed to perform a safety assessment, study staff will record the date, clinician initials, and comments related to the suicidality assessment

in the Study Trax C-SSRS module. Following the initial suspicion or identification of self-harm and/or suicidality, a study clinician will follow up with the participant on the current nature of their situation, querying about any new ideation, intent, and/or plan since the last visit. These clinicians, along with the PI will then determine whether a participant can safely continue the study. If the clinicians determine that the participant cannot safely continue the study, the participant will be discontinued, and will be provided with a list of resources for follow-up care.

Blood tests: a trained member of the study staff will draw venous blood (up to 10 ml) from all subjects in order to have them genotyped for the **Ala147Thr TSPO polymorphism** in the *TSPO* gene (rs6971) (unless this genotype information is already available), and to check liver enzyme values. Additionally, during screening for eligibility, we will conduct routine chemistry and LFT/GGT. We will obtain serum transaminases (ALT and AST) and total bilirubin levels in all patients prior to starting treatment with CBD.

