While [\$^{11}C\$]PBR28 has the advantage of binding to the TSPO protein with a higher ratio of specific-to-nonspecific binding than [\$^{11}C\$](R)PK11195\$^{47}, it also presents a potential limitation, in that about 10% of human subjects show no binding to PBR28\$^{48}\$ (whereas [\$^{11}C\$](R)-PK11195\$ has never been associated with non-binding\$^{49}\$). A recent study has demonstrated that the rs6971 polymorphism predicts PBR28 binding affinity in human platelets\$^{50}\$. Since the low-affinity binder phenotype is consistent across all tissues within the same subject \$^{49}\$, testing for the Ala147Thr polymorphism has been suggested to predict low affinity for [\$^{11}C\$]PBR28 in all organs, including the brain. High or Mixed affinity binders (Ala/Ala or Ala/Thr) will be considered eligible, whereas the Low affinity binders (Thr/Thr) will be considered ineligible for the research study. The MGH lab responsible for genotyping typically runs the genotyping assay only twice per month, requiring that we normally schedule screening and scanning visits approximately two weeks apart.

An additional 10 mL of venous blood will be collected and stored for future investigations on the roles of genetic, molecular, and cellular factors in pain disorders. This will include the future possibility to generate induced pluripotent stem cells (iPSCs) from peripheral blood mononuclear cells⁵¹⁻⁵³ to assess in-vitro alterations in patient-derived neural or glial cells^{54,55}.

Urine drug test: We will also perform a urine test to screen for use of opioids and illicit drugs (including amphetamine, barbiturates, cocaine, marijuana, etc.). The urine drug screen will be performed during the screening visit. A rapid urine drug screening that utilizes monoclonal antibodies to detect elevated levels of specific drugs in urine, will be used for this purpose. Results will be read five minutes after the test was started.

MR-PET visits

Participants eligible to continue into the study based on the screening visit and initial blood test will be asked to participate in a first MR-PET visit.

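### Patients with normal baseline liver enzymes and no symptoms have no scheduled liver test during the 28 days of CBD dosing, so the discontinuation rule cannot act on a silent elevation that meets both of its thresholds

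*Combined protocol and SAP*

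**What the plan says.** Liver testing is described in several parts of the protocol.

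- **Before treatment, all patients** (Blood tests, under the screening visit): "We will obtain serum transaminases (ALT and AST) and total bilirubin levels in all patients prior to starting treatment with CBD".
- **Week 2, some patients** (Risks and Discomforts, paragraph on Epidiolex): those who, before treatment, "had elevated AST/ALT levels but still met the eligibility criteria for the study will undergo a follow-up liver function tests at 2 weeks".
- **Any time, if prompted** (Risks and Discomforts; Monitoring and QA): clinical signs or symptoms pointing to the liver lead to prompt testing, and to interruption or discontinuation as appropriate. The examples given include nausea, vomiting, right upper quadrant pain, fatigue, anorexia, jaundice and dark urine.
- **Week 4, all patients** (Follow-up Visits): "We will also take a small sample of blood for a follow-up liver function test". This takes place at a "second follow-up appointment immediately after the four-week treatment period".

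The week-2 visit for all patients is with a study clinician, "where health and adverse events will be assessed, and patients will complete questionnaires and will be reminded to increase medication dose". No blood draw is listed for it.

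Dose and Exposure sets the titration at "5 mg/kg/d in week 1, 10 mg/kg/d in week 2, 15 mg/kg/d in week 3, and 20 mg/kg/d in week 4".

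Monitoring and QA sets two liver rules on the same joint criterion of transaminases above 3 times ULN and bilirubin above 2 times ULN. CBD is discontinued in any patient who meets it, and the study stops if 2 or more patients do.

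**The concern.** A rule for stopping the drug in an individual patient needs a laboratory result obtained while the drug is still being taken. For patients with normal baseline enzymes, the plan supplies one only if signs or symptoms appear. If a patient meets both thresholds silently, the first scheduled result comes when there is no drug left to stop. In between, the dose has been raised three times, and at week 2 the patient is reminded in person to raise it without a liver result in hand.

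What is at stake is avoidable exposure in a trial that, under Potential Benefits, expects little benefit for the individual participant.

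**Working it through.** The plan gives no figure to reproduce here. The check sets the testing schedule against the dosing period and then works out the dose involved.

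**Step 1: scheduled liver tests during the 28 dosing days, no signs or symptoms.**

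- Normal baseline AST/ALT: 0. The tests fall before the first dose and at the visit after the last week of dosing.
- Elevated baseline AST/ALT but eligible: 1, at week 2.

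Nothing else in the protocol fills the gap. Blood taken at the scan visits is for substances such as cytokines (MR-PET visits), and those visits bracket the dosing period. The daily survey concerns the treatment's effect on pain (Study Procedures).

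**Step 2: planned cumulative dose**, from the titration schedule at full dose, 7 days per step.

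- Total: 7 × (5 + 10 + 15 + 20) = 350 mg/kg.
- Taken by day 14: 7 × (5 + 10) = 105 mg/kg; 105/350 = 30%.
- Remaining after day 14: 7 × (15 + 20) = 245 mg/kg; 245/350 = 70%.
- Remaining after day 21, that is, the 20 mg/kg/day week: 7 × 20 = 140 mg/kg; 140/350 = 40%.

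**Step 3: dose avoided by acting on a week-2 sample**, taking the visit as day 14.

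- Stopped before the step to 20 mg/kg/day: 140 mg/kg (40%).
- Result available after an assumed 1 day: 245 − 15 = 230 mg/kg (66%).
- Result available after an assumed 3 days: 245 − 3 × 15 = 200 mg/kg (57%).
- Stopped at day 14 itself, the upper limit: 245 mg/kg (70%).

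The 1- to 3-day delay is an assumption; the protocol gives no turnaround time for the liver panel. All four figures apply only to an elevation that already meets both thresholds at week 2.

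**Step 4: interval.** With a week-2 test for everyone, the longest scheduled stretch of dosing without a liver test falls from 28 days to about 14.

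**The case against.** The strongest reply is that this is a deliberate, risk-based schedule. Risks and Discomforts attributes the hepatic events seen with CBD largely to interaction with anti-epileptic drugs. Those are excluded, as are valproate and clobazam by name and a long list of interacting medicines. The week-2 test is then aimed at the patients with a visible reason for concern. This lowers the expected risk, and that part stands. But the attribution is stated only as likely, and the protocol still keeps a discontinuation rule for any patient. A rule kept for everyone should have data for everyone.

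The symptom trigger is also broad. Jaundice and dark urine are on the list and bear directly on the bilirubin half of the criterion. This narrows the gap to patients who meet both thresholds with none of the listed signs. It does not close it. Fatigue and decreased appetite are also reported effects of the drug, and tiredness is a listed reason for a 5 mg/kg dose reduction, so such complaints could be read as poor tolerability and not lead to a liver test.

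Nor is the week-4 test empty. It cannot stop a finished course, but its result can count toward the study-level stop and so protect later patients.

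Three stronger readings are tempting, and the documents do not support them.

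- *Any silent rise in ALT or AST escapes the rule for want of a test.* The rule requires the bilirubin threshold too. An isolated transaminase rise would not trigger it even with a week-2 test.
- *Patients are on drug for about six weeks between tests.* Screening and scanning are set apart by genotyping, "requiring that we normally schedule screening and scanning visits approximately two weeks apart", and Study Procedures says of the first imaging visit "At this visit, subjects will receive CBD". On that reading the two tests are about 14 + 28 = 42 days apart, but the first 14 precede any dose. The Drug Administration Protocol instead places the start of CBD after the behavioral visit. The relevant period is the 28 days of dosing.
- *The percentages of dose avoided measure harm.* They measure drug not taken, given a qualifying elevation. They say nothing about how often one occurs.

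**Conclusion.** The gap is real and limited. A patient with normal baseline enzymes and no signs or symptoms has no scheduled liver test during dosing, so the individual discontinuation rule cannot act in that period on an elevation that meets both thresholds silently. For such an elevation present at week 2, between 140 mg/kg (40%) and at most 245 mg/kg (70%) of the planned 350 mg/kg could be avoided, depending on how soon the result is acted on. This assumes full titration without dose reduction and a week-2 visit at day 14.

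The documents give no rate of silent qualifying elevations, so no expected number of cases is claimed; it is likely to be small. Confidence is high on the testing schedule and not on the clinical consequence. The change is worth making because it is cheap, not because harm has been shown to be likely.

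**What to change.** Take ALT, AST and total bilirubin from every patient at the existing 2-week visit. Have a study physician review the result as soon as it is available, and no later than the step to 20 mg/kg/day, and apply the discontinuation rule in Monitoring and QA to it. Leave the week-4 test, the thresholds, the symptom-triggered testing and the study-level stops unchanged.

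The cost is one small blood draw and panel for each dosed patient with normal baseline enzymes; those with elevated values already have it. The plan is for 20 completers, so the number dosed may be somewhat higher. No new visit is needed. Some mild elevations will call for a repeat test.

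Two limits remain. Isolated transaminase rises still do not meet the joint rule, although the physician would see them. Elevations that begin only at 15–20 mg/kg/day are still not seen until week 4 unless they cause signs or symptoms.
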